9.2.2 Secondary Endpoints

- Components of the primary endpoint:
 - Proportion of eyes with CRR of VA from Baseline at Month 12 compared to matching external natural history control group
 - Proportion of eyes in which Baseline VA better than 1.0 logMAR was maintained at Month 12 compared to matching external natural history control group
- Proportion of eyes in patients treated with idebenone >1 year after the onset of symptoms with CRR of VA from Baseline or in which Baseline VA better than 1.0 logMAR was maintained at Month 12 compared to external natural history control group, in all patients and classified by mutation
- Proportion of eyes and patients treated with idebenone ≤1 year after the onset of symptoms with CRR of VA from Baseline or in which Baseline visual acuity better than 1.0 logMAR was maintained following 6, 18 and 24 months of treatment with idebenone compared to matching external natural history control group, in all patients and classified by mutation
- Proportion of eyes/patients treated with idebenone ≤1 year or >1 year after the onset of symptoms with "Off-chart" VA at Baseline in whom VA improves to better than 1.60 logMAR by Month 6, 12, 18 and 24
- Proportion of eyes/patients treated with idebenone ≤1 year or >1 year after the onset of symptoms with VA in the categories of better than 1.0 logMAR, 1.0 to 1.68 logMAR and above 1.68 logMAR at each assessment time point up to Month 24
- Safety as assessed by AE count and laboratory analyses during the study

The external natural history control group for the eyes with Baseline >1 year after the onset of symptoms in the OLS will be generated as follows:

- All available eyes in the external natural history dataset will be considered, regardless of whether the eye in question was used in the control group for the primary objective or not
- All VA assessments data collected >1 year after the onset of symptoms are considered as potential baseline values
- If a potential baseline value does not have a follow-up VA assessment within 12±3 months, it will be excluded
- The remaining potential baseline values will be categorized in the following time since onset bins: between >1-2 years, >2-3 years, >3-4 years or >4-5 years
- If there are several potential baseline values for the same eye in the same bin, the eye with the baseline value closest to the midpoint of the bin will be selected

- The selected baseline value and the follow-up VA assessment within12±3 months in the same eye will be included in the external natural history control group for the eyes in the OLS with baseline >1 year after the onset of symptoms
- It should be noted that different cuts (various baseline with corresponding follow-up VA values) from the same eye can be used multiple times, both for the analysis of the primary endpoint (only once) and for the analysis of eyes with baseline >1 year after the onset of symptoms (not more than once within each of the four bins defined above)

9.2.3 Safety Variables

Safety will be assessed based on a series of parameters, including:

- Adverse events/AESIs
- Physical examinations
- Vital signs
- Clinical laboratory values (haematology, biochemistry and urine analysis)

9.3 Analysis Populations

9.3.1 Intent-To-Treat Population

The Intent-To-Treat (ITT) population will include all enrolled patients who received at least one dose of the study medication and provide at least one post-baseline VA assessment and are confirmed carriers of only one of the three major LHON mtDNA: G11778A, G3460A or T14484C.

9.3.2 Safety Population

The Safety Population will include all enrolled patients who received at least one dose of study medication.

9.4 Analysis Methods

9.4.1 Analysis of Demographic and Baseline Characteristics

Demographic and Baseline characteristics will be summarized with descriptive statistics.

Demographic and Baseline analysis will be performed on the Intention-To-Treat population.

9.4.2 Efficacy Evaluation

The primary analysis will be based on Intention-To-Treat principle as change from Baseline.

The primary endpoint will be analysed using a logistic regression model. The binary response will be used as the dependent variable. The independent variables include the treatment group (idebenone treated patients versus untreated control group) and mutation group (G11778A, G3460A, T14484C). The difference between the idebenone treated patients versus untreated control group will be estimated with odds ratio estimates, 95% confidence intervals and two-sided p-values.

All patients who have at least one post-baseline assessment at 12±3 months after Baseline will be included in the primary analysis. This approach is chosen due to the lack of pre-defined visit structure in the control dataset. As a sensitivity analysis, the impact of incomplete data will be assessed by analysing the primary endpoint with a generalized linear mixed model. For this purpose, the SAS GLIMMIX procedure for binomial data with logic link will be used to estimate the treatment differences. Factors similar to the ones used for the primary endpoint will be included in the model. The data from the control dataset will be classified as visits by selecting the assessment which is closest to 6, 12, 18 and 24 months from all assessments conducted within a window of ±3 months. The treatment difference at Month 12 will be estimated using contrasts.

The secondary endpoints based on counts of eyes/patients will be analysed with methods similar to the primary endpoint.

The baseline VA will be used as a covariate and treatment group and mutation as fixed factors. A mixed model for repeated measures (MMRM) will be used to assess the impact of incomplete data. The responder status (CRR or no CRR) will be used as independent variable instead of the treatment group, as this data are not available in the control dataset.

At least the following subgroups will be analysed:

• Each primary LHON mtDNA mutation separately (G11778A, G3460A, T14484C)

9.4.3 Safety Evaluation

The disposition of the patients will be summarized by tabulating the number of enrolled, completed and discontinued patients. The reasons for premature discontinuations will be tabulated. The extent of exposure will be summarized by tabulating the duration of the study treatment.

All adverse events (AEs) will be coded using the MedDRA dictionary. The treatment-emergent AEs (i.e., events which start or worsen during the study treatment) will be tabulated by system organ class and preferred term. Both subject and event counts will be calculated. In addition, the treatment-emergent AEs will be evaluated by severity and by relationship to the study treatment. The serious AEs and AEs leading to a premature discontinuation will also be summarized.

The clinical laboratory variables and vital signs will be summarized descriptively, including a tabulation of normal and abnormal values.

9.5 Analyses

The final analysis for the primary endpoint will be conducted at the time when all subjects enrolled in this open label intervention study have completed Visit 6/Month 12. The following efficacy and safety parameters will be reported:

Efficacy (primary endpoint):

Proportion of eyes in patients treated with idebenone ≤1 year after the onset of symptoms with CRR of VA from Baseline or in which Baseline VA better than 1.0 logMAR was maintained at Month 12, compared to matching external natural history control group

Safety (secondary endpoint):

The count of patients who experienced abnormal biochemistry, haematology and/or urine test results will be reported, compared to the Baseline assessments.

A detailed analysis plan will be prepared as part of the SAP prior to database lock.

Final analyses will be conducted and a Clinical Study Report prepared when the last patient has left the study.

9.6 Sample Size and Power Considerations

The present study is designed to provide sufficient statistical power for a pre-planned indirect comparison of the primary endpoint against an external natural history control group.

As defined in the original LEROS study protocol (Version1.0, 29 January 2016, Section 9.6), the sample size calculation for LEROS assumed an expected 24% responder rate in the external natural history control group (combined data from SNT-IR-006 and SNT-CRS-002). The protocol defines a pre-planned check of the estimate of responder rate in the control group, once the enrolment of the new natural history study (SNT-CRS-002) has been completed. In case the responder rate in the control group is different from 24%, a sample size re-calculation using the updated control group estimate can be considered.

As SNT-CRS-002 study was completed, the data collected in the natural history studies has now been checked for the estimate of the responder rate. Based on the combined data from 175 eyes in the two natural history studies (SNT-IR-006 and SNT-CRS-002), the estimated responder rate is below 22%, i.e. lower than the initially expected rate of 24%. Although the determination of the exact responder rate for the natural history studies requires final data from the LEROS study for matching purposes, it is reasonable to assume that the responder rate of the natural history studies is not higher than 22%. The sample size for LEROS study is therefore re-calculated using the same methods as in the original protocol (Version1.0, 29 January 2016). In order to reach a power of 90% for the comparison of the responder rates between the natural history studies (assumed to be 22% instead of 24%) and the LEROS study (assumed to be 40%, as defined in the protocol), evaluable data from altogether 110 eyes from the LEROS study is required. In order to account for a drop-out rate of 30% (as defined in the protocol), at least 80 patients (equal to 160 eyes) will be enrolled to the LEROS study.

The sample size calculation was done with nQuery Advisor version 8.3.

For the sample size for the eye treated >1 year after the onset of symptoms and the corresponding external natural history control group, the aim is to collect VA data from same number of eyes as for the primary objective in order to compare the patients treated ≤1 and >1 year since the onset of symptoms and to compare patients treated with Raxone >1 year since the onset of symptoms with the corresponding natural history control group, assuming sufficient natural history control data can be collected to generate the natural history control group as described in 9.2.2.

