idebenone therapy and CRR, where possible compared to untreated control patients.

The treatment duration in RHODOS was 6 months and a larger proportion of idebenone-treated patients presented with CRR in VA compared to placebo. However, data from Santhera's ongoing Expanded Access Program (EAP) indicates that prolonged treatment can increase both the proportions of patients with CRR of VA and the magnitude of the recovery observed. Furthermore, data from the RHODOS and from the EAP provide evidence that the LHON-causative mutation harboured is prognostic of CRR in VA. Therefore, secondary objectives of this study are to provide information on the effect of treatment duration on both the proportions of patients presenting with CRR and on the magnitude of any response with increasing treatment time and on the influence of the mutation harboured on CRR rate compared to spontaneous CRR (sCRR) in untreated control patients.

The study will also allow the assessment of the safety and tolerability of long-term treatment with idebenone, with particular emphasis on the proportion of patients experiencing elevated Liver Function Tests (LFTs) or changes in blood cell counts.

Number of Centres

Approximately 35

Multinational study with US sites operating under IND and EU sites not operating under IND.

Number of Patients

80 patients presenting ≤1 year after the onset of symptoms will be enrolled to ensure 61 provide VA assessments following 12 months of idebenone treatment (primary endpoint).

80 patients presenting >1 year after the onset of symptoms will be enrolled to ensure 61 provide VA assessments following 12 months of idebenone treatment (secondary endpoint). Patients will be stratified according to time since onset of symptoms with a maximum of 30 patients to be enrolled in any of the strata of >1 - \leq 2 years, >2 - \leq 3 years, >3 - \leq 4 years and >4 - \leq 5 years since onset of symptoms.

Inclusion Criteria

- 1. Impaired visual acuity in affected eyes due to LHON
- 2. No explanation for visual loss besides LHON
- 3. Age \geq 12 years
- 4. Onset of symptoms ≤5 years prior to Baseline
- 5. Confirmation of either G11778A, G3460A or T14484C LHON mtDNA (for the ITT population, not required for enrolment)
- 6. Written informed consent obtained from the patient
- 7. Ability and willingness to comply with study procedures and visits

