Proportions of Patients and Eyes in the EAP with CRR from VA Nadir following 6 months and 12 months of treatment

CRR from Nadir	Patients		Eyes		Treatment duration at assessment [months]			
in the Efficacy Population	all	CRR	all	CRR	mean	(SD)	min	max
Patients with 6m assessment available	62	CRR at 6m 19 (30.6%)	124	CRR at 6m 30 (24.2%)	5.8	(1.0)	3.1	8.1
12m assessment available	47	CRR at 12m 17 (36.2%)	94	CRR at 12m 28 (29.8%)	11.6	(1.3)	9.1	13.9
at last observation	69	CRR at last obs. 34 (49.3%)	138	CRR at last obs. 55 (39.9%)	15.4	(9.0)	2.8	36.2

6m assessment : closest to 6 months, values at 3-9 months considered

12m assessment: closest to 12 months, values at 9-15months considered

Source Tables : EAP 01-01, EAP 01-02, EAP 01-03, EAP 02-01, EAP, 02-02, EAP 02-03

Magnitude of Recovery in Eyes in the EAP with CRR from VA Nadir at the 6 month, 12 month or at the last observation

Recovery* from Nadir [logMAR]**	N	mean	SD	median	max	min
at the 6 month vist	15	-0.47	0.31	-0.38	-1.00	-0.14
at the 12 month vist	15	-0.62	0.48	-0.40	-1.40	-0.10
at last observation (mean treat. dur. 20.9 m)	15	-0.93	0.42	-1.08	-1.44	-0.14

^{*}for eyes with CRR from BL where recovery had occured at the 6 months visit and a 12 month visit was available, too

Note, for these 15 eyes the VA at BL was also the VA at Nadir

Furthermore, data from the RHODOS and from the EAP provide evidence that the LHON-causative mutation harboured is prognostic of CRR in VA.

Therefore, secondary objectives of this study are to provide information on the effect of treatment duration on both the proportions of patients presenting with CRR and on the magnitude of any response with increasing treatment time and on the influence of the mutation harboured on CRR rate compared to spontaneous CRR (sCRR) untreated control patients.

The study will also allow the assessment of the safety and tolerability of long-term treatment with idebenone, with particular emphasis on the proportion of patients experiencing elevated Liver Function Tests (LFTs) or changes in blood cell counts.

^{**}off chart set to 1.70 [logMAR]

2 Study Objectives and Endpoints

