3.1 Summary of Study Design

The study will be an open-label interventional study requiring 80 patients enrolled ≤1 year after the onset of symptoms to complete the 12 month treatment period (for evaluation of the primary endpoint), and 80 patients enrolled >1 year after the onset of symptoms to complete the 12 month treatment period (for evaluation of the secondary endpoints in these patients).

This multinational study is conducted with one protocol for sites under the IND (U.S. sites) in compliance with the IND requirements contained in 21 CFR 312, and a different version of the protocol for foreign sites not under the IND. As the intent is to pool the data from U.S. and foreign sites, it is ensured, as required, that the protocol versions are very similar or identical.

Patient eligibility for enrolment will be determined during the Baseline (Visit 1). Beginning at Baseline (Visit 1), the patient will receive study medication to take at home and will undergo regular assessments in the clinic throughout the study period until Visit 8 (Month 24) at which time the study medication is withdrawn. For all patients, there will be a final follow-up 28-35 days after study medication withdrawal. Patients enrolled in the study will commence study medication intake on the first day after the Baseline visit.

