9.2 Analysis Variables

9.2.1 Primary Endpoint

[figure not shown]
 Proportion of eyes with clinically relevant recovery of VA from Baseline or in which Baseline VA better than 1.0 logMAR was maintained at Month 12, compared to matching external natural history control group

CRR of VA is defined below and illustrated in Figure 1:

- For any "off-chart" VA category (CF, HM, LP or NLP), CRR in VA is defined as the ability to read at least 5 letters "on-chart" (the equivalent of one full chart line) at the last available assessment
- For "on-chart" VA, CRR in VA is defined as the ability to read at least 10 additional letters (equivalent to two chart lines) at the last available assessment

Figure 1: VA categories

CRR from Baseline for eyes (treated independently) and for patients (with at least one eye with CRR) will be determined.

Proportion of eyes with CRR of VA from Baseline or in which Baseline VA better than 1.0 logMAR was maintained at Month 12, will be compared to a matching external natural history control group which is generated as defined below.

Data from the previously conducted Case Record Survey (CRS; SNT-IR-006) and from the newly ongoing CRS (SNT-CRS-002) will be used to generate a combined CRS control dataset which will be applied as an external natural history control group for comparison against patients treated with idebenone in this open label study. All patient VA data in the combined CRS control dataset will have VA values observed at a known time since the onset of symptoms and all VA data subsequently captured, regardless of the assessment time, will be included in the combined CRS database. This approach will be used to compare data collected in this open label study to the combined CRS idebenone naïve patients control dataset for the primary endpoint.

In order to optimize the comparability of patient data in the combined CRS control dataset to this open label study for the primary endpoint, a subgroup of patient VA data points from the CRS control dataset will be prospectively defined as follows:

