As SNT-CRS-002 study was completed (Clinical Study Report version 1.0 dated 15 July 2019), the data collected in the natural history studies has now been checked for the estimate of the responder rate. Based on the combined data from 175 eyes in the two natural history studies (SNT-IR-006 and SNT-CRS-002), the estimated responder rate is below 22%, i.e. lower than the initially expected rate of 24%. Although the determination of the exact responder rate for the natural history studies requires final data from the LEROS study for matching purposes, it is reasonable to assume that the responder rate of the natural history studies is not higher than 22%. The sample size for LEROS study is therefore re-calculated using the same methods as in the original protocol (Version1.0, 29 January 2016). In order to reach a power of 90% for the comparison of the responder rates between the natural history studies (assumed to be 22% instead of 24%) and the LEROS study (assumed to be 40%, as defined in the protocol), evaluable data from altogether 110 eyes from the LEROS study is required. In order to account for a drop-out rate of 30% (as defined in the protocol), at least 80 patients (equal to 160 eyes) will be enrolled to the LEROS study.

The sample size calculation was done with nQuery Advisor version 8.3.

For the sample size for the eye treated >1 year after the onset of symptoms and the corresponding external natural history control group, the aim is to collect VA data from same number of eyes as for the primary objective in order to compare the patients treated ≤1 and >1 year since the onset of symptoms and to compare patients treated with Raxone >1 year since the onset of symptoms with the corresponding natural history control group, assuming sufficient natural history control data can be collected to generate the natural history control group as described in 8.3.2.

Study: SNT-IV-005

V1.0 07 June 2021

7 Statistical hypotheses

The primary aim of the analysis is to show the superiority of Raxone® (patients treated ≤1 year after onset of symptoms) versus matching NH IDE naïve patients in proportion of eyes with clinically relevant recovery of VA from BL or 12 month maintenance of BL VA better than 1.0 logMAR

H₀: Raxone® (patients treated ≤1 year after onset of symptoms) is not superior to matching NH IDE naïve patients in proportion of eyes with CRR of VA from BL or 12 month maintenance of BL VA better than $1.0 \log MAR$

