12.1 Primary endpoint

Endpoint: Proportion of eyes with clinically relevant recovery (CRR) of visual acuity from Baseline (BL) or in which BL VA better than 1.0 logMAR was maintained at Month 12 in patients treated with Raxone® ≤1 year after the onset of symptoms, compared to matching external natural history control group. CRR definition is presented in section 16.

Analysis sets: Primary endpoint analysis will use all LEROS mITT eyes that are ≤1 year since onset of symptoms at BL and have the Month 12 assessment. External NH control set is generated as described in section 8.5.1 (Matching algorithm for the primary endpoint), using VA assessments within 12±3 months from BL.

Analysis method: The primary endpoint will be analysed using a logistic regression model. The binary response will be used as the dependent variable. The independent variables include the treatment group (Raxone® treated patients versus untreated control group), gender (male, female) and mutation group (G11778A, G3460A, T14484C) as fixed factors.

The difference between the Raxone® treated patients versus NH group will be estimated with odds ratio, two-sided 95% confidence intervals and two-sided p-values

```
proc logistic;
  class treatment gender mutation / param=ref;
  model CRB(event='1') = treatment mutation gender / link=logit clodds=pl;
  oddsratio treatment;
run;
```

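### The 90% power for 110 LEROS eyes counts fellow eyes as independent; a test that holds 5% has about 70–80% power at the fellow-eye correlation in the protocol's own EAP table

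*Protocol*

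**What the plan says.** Protocol 9.6 and SAP 6 compare an assumed 22% responder rate in the natural history controls with 40% in LEROS at 90% power, and conclude that "evaluable data from altogether 110 eyes from the LEROS study is required". The control rate comes from existing data: "Based on the combined data from 175 eyes in the two natural history studies". Allowing for 30% drop-out, "at least 80 patients (equal to 160 eyes) will be enrolled to the LEROS study" (SAP 6). Neither section mentions within-patient correlation, a design effect or the number of control patients.

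Protocol 9.2.1 states "CRR from Baseline for eyes (treated independently) and for patients (with at least one eye with CRR) will be determined". The primary model in SAP 12.1 is an ordinary logistic regression with one record per eye: "model CRB(event='1') = treatment mutation gender / link=logit clodds=pl". It has no patient effect and no clustered variance. SAP 7 declares superiority if the lower limit of the two-sided 95% confidence interval for the odds ratio exceeds 1.

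The evaluable number is also given differently elsewhere. The Protocol synopsis says 80 patients "will be enrolled to ensure 61 provide VA assessments following 12 months of idebenone treatment", and Protocol 3.1 describes a study "requiring 80 patients enrolled ≤1 year after the onset of symptoms to complete the 12 month treatment period".

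**The concern.** Two eyes of one LHON patient share the mutation, age, time course and treatment. Protocol 1.1 says over 97% of patients have second-eye involvement within 12 months. If fellow eyes tend to respond together, 110 eyes from about 55 patients carry less information than 110 independent eyes.

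Two consequences follow. The stated 90% is not the power of any test of these data that holds a 5% level. And the planned model's confidence interval is too narrow, so the SAP 7 rule does not operate at 5%. A reader relying on 9.6 would misjudge how much either a positive or a negative primary result shows.

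**Working it through.** **1. Reproduce the stated figure.** Inputs: control rate 0.22, LEROS rate 0.40, 110 LEROS eyes (Protocol 9.6); two-sided 5% (SAP 7). The control number is not named as an input; 175 is assumed because 9.6 gives it for the control data.

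- Pooled rate = (175×0.22 + 110×0.40)/285 = 0.2895.
- Null SE = √[0.2895×0.7105×(1/175 + 1/110)] = 0.0552.
- Alternative SE = √[0.22×0.78/175 + 0.40×0.60/110] = 0.0562.
- Power = Φ[(0.18 − 1.96×0.0552)/0.0562] = Φ(1.28) = 89.9%.

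The smallest LEROS number reaching 90% is 111. With 150 control eyes it would be about 125, and with 200 about 102, so 175 fits. The drop-out step also agrees: 110/0.70 = 157.1, or 158 eyes, close to the 160 enrolled. No design effect enters anywhere.

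**2. Fellow-eye correlation from the EAP table (Protocol 1.2).** Eyes are exactly twice patients, and a responding patient has at least one responding eye. So patients with both eyes responding = responding eyes − responding patients, and ICC = [P(both) − p²]/[p(1 − p)], where p is the eye-level rate.

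| Time point | Patients | Responding patients | Responding eyes | Both eyes | p | ICC |
|---|---|---|---|---|---|---|
| 6 months | 62 | 19 | 30 | 11 | 0.242 | 0.648 |
| 12 months | 47 | 17 | 28 | 11 | 0.298 | 0.695 |
| Last observation | 69 | 34 | 55 | 21 | 0.399 | 0.607 |

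At 12 months independent eyes would give 47×0.298² ≈ 4 patients with both eyes responding; the table implies 11.

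**3. Power at a true 5% level.** Divide the eyes in each paired group by the design effect 1 + ICC and repeat step 1. For the 12-month ICC with both groups paired, both SEs grow by √1.695 = 1.302, to 0.0718 and 0.0732. Then (0.18 − 1.96×0.0718)/0.0732 ≈ 0.535, so power is 70.4%.

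**4. What the planned model does.** It keeps the unadjusted critical value while the true variance is larger by 1 + ICC in each paired group. With both groups paired, type I error = 2[1 − Φ(1.96/√(1 + ICC))].

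| ICC | Valid 5% test: both paired | Valid 5% test: LEROS only | Planned model type I: both paired | Planned model type I: LEROS only |
|---|---|---|---|---|
| 0 | 89.9% | 89.9% | 5.0% | 5.0% |
| 0.3 | 81.2% | 84.9% | 8.6% | 7.2% |
| 0.5 | 75.5% | 81.5% | 11.0% | 8.6% |
| 0.607 | 72.6% | 79.8% | 12.2% | 9.4% |
| 0.648 | 71.6% | 79.1% | 12.7% | 9.7% |
| 0.695 | 70.4% | 78.4% | 13.2% | 10.1% |

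At the three EAP correlations, under the assumed effect, the planned model rejects 83.7–84.3% of the time with both groups paired and 85–86% with LEROS only.

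**5. Simulation check** (100,000 trials per setting, 55 LEROS pairs, Wald test on the log odds ratio). At the three EAP correlations a patient-clustered test had 70.0–72.4% power with paired controls and 78.1–79.6% with unpaired controls, with type I error 4.6–4.8%. The unclustered test had type I error of 12.0–13.0% and 9.2–9.7% respectively.

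**6. Other assumptions.** If the control rate is 20%, power with both groups paired at the EAP correlations is 80–82%; at 18% it is 88–89%. If half the pairing effect applies in both groups (design effect 1 + ICC/2), power is about 80% at ICC 0.65 and 83% at 0.5.

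**7. Evaluable numbers.** 80×0.70 = 56 patients, or 112 eyes. The synopsis figure of 61 implies retention of 61/80 = 76%, not 70%.

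**The case against.** The strongest reply concerns size.

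- **Proxy correlation.** The EAP figures come from overlapping subsets of one treated cohort and measure recovery from nadir, not the composite from baseline. A multinomial bootstrap gives 95% intervals of about 0.38–0.85, 0.43–0.90 and 0.40–0.79.
- **Covariates.** The primary model adjusts for mutation and gender, both patient-level. Protocol 1.2 calls mutation prognostic, so part of the raw correlation may be explained. The documents do not allow the residual correlation to be calculated.
- **Pairing.** Eyes are selected eye by eye (SAP 8.5.1 and 12.1), so full pairing is an upper case even within LEROS.
- **Control rate.** 9.6 treats 22% as a ceiling; a lower rate raises power (step 6).
- **Inputs.** The method is referred back to protocol Version 1.0, which is not available. A 1:1 one-sided 5% calculation gives 112 eyes per arm, also near 110. The 9.2.1 wording on independent eyes can be read as a rule for deriving the endpoint, not as a variance assumption.
- **Timing.** The SAP is dated June 2021 and SAP 12.4 already describes Month 12 attendance, so restating power changes no enrolment decision.

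The first four points make 70–80% an illustrative range. None reverses the direction: even at ICC 0.3 with both groups paired, power is 81% and the planned model's type I error is 8.6%. The one-sided reading has no design effect either and conflicts with the two-sided rule in SAP 7. The timing point is fair for the power text, but the variance in SAP 12.1 still determines the primary confidence interval. The sensitivity analyses do not cover it: the mixed model in Protocol 9.4.2 addresses incomplete data and names no patient effect, and the SAP 12.1.1 analyses reuse the unclustered model.

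**Conclusion.** The concern holds. The stated 90% is an independent-eyes figure. With 22% versus 40% and 110 versus 175 eyes, any positive fellow-eye correlation puts the power of a valid 5% test below 90%. At the EAP correlations it is about 70–73% if both groups are fully paired and 78–80% if only LEROS eyes are. The planned model's type I error would be about 12–13% or 9–10% respectively.

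These sizes rest on the EAP correlation as a proxy, 55 complete LEROS pairs, 175 as the control number, undocumented pairing among controls, and no covariate adjustment. The independence assumption is inferred from the reproduction and from the absence of any design effect; the documents do not state it.

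The mismatch between 56 and 61 evaluable patients, and wording that can be read as 80 completing rather than 80 enrolled, are editorial. The figure of 61 may reflect another drop-out convention (80/1.30 = 61.5). Both 56 and 61 exceed the 55 patients needed, so no shortfall follows.

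**What to change.** 1. **Protocol 9.6 and SAP 6.** State that 90% assumes independent eyes. Add the power of a patient-clustered analysis at two-sided 5% over a range of correlations: about 81% and 75% at ICC 0.3 and 0.5 with both groups paired; about 70–73% at 0.61–0.69 with both paired, or 78–80% with only LEROS paired. Cite the EAP table as the source and note its limits: treated patients, recovery from nadir, small samples.
2. **SAP 12.1.** Keep the covariates, but estimate the primary model with a patient-clustered variance (GEE or cluster-robust standard errors with patient as the cluster). Replace the profile-likelihood limits with limits based on that variance, and carry the option into the analyses that reuse this model.
3. **Editorial.** Reconcile the synopsis figure of 61 with 9.6 (56 patients, 112 eyes), and make clear in Protocol 3.1 and SAP 5 that 80 is the number enrolled.

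The cost is text in five places and a change of variance estimator in the code. The imputation code takes its standard errors from the profile-likelihood limits, so it would need the matching change. No new data or patients are required. The stated power falls and the primary confidence interval will probably widen.
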